10.3.2 Analysis of Secondary Outcome Measures

Secondary outcomes will be analysed using suitable regression models (e.g. linear regression for continuous outcomes and ordinal regression for ordinal data).

10.3.3 Mechanistic analysis

We will conduct a range of analyses that will explore the mechanism of ECP.

1. To investigate which cell and molecular variables in blood (at baseline) are associated with response, we will fit regression models with responder/non-responder as an outcome and each potential biomarker included (in a separate model) as a baseline covariate.
2. To investigate the trajectories of the cell and molecular variables and how they differ in responders and non-responders, we will fit a longitudinal model for each variable with responder/non-responder as a covariate. This will be done in all patients and then separately in SOC and SOC+ECP patients.
3. To investigate the differential composition of circulating leukocytes, we will model the percentage of blood made up of each cell type and how these change from baseline over time in responders and non-responders using a longitudinal model as described above.
4. To investigate if differences in the transcriptional signature of leukocytes at baseline or changes over time are predictive of response, we will perform both single gene and effector pathway analysis in responders and non-responders across both study arms.
5. To investigate if there is a predictive signature associated with the treatment effect of ECP+SOC vs SOC, we will apply a method developed in Newcastle that extends the adaptive signature design (323). This may detect a 'sensitive' subgroup of patients who strongly benefit from ECP.

These analyses will be exploratory and will help inform a subsequent effectiveness study. The power of the mediation analyses depends on the proportion of responders and non-responders. Assuming

50% of patients are responders, we will have 90% power to detect standardised effect sizes of 0.7. For the Newcastle site, we anticipate a sample size of around 16, which would provide 90% power to detect standardised differences of 1.6. A multiple testing correction will be applied to ensure that the false discovery rate is controlled at 5%.

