	Absolute change in lung allograft function	FEV1 and FVC
	Change in exercise capacity at 24 weeks	6-minute walk test

	Change in Quality of Life measurements at 24 weeks	EQ-5D-5L and SF-36 v2 questionnaires
	Change in Disease severity	ISHLT CLAD Stage
	Survival at 24 weeks	
Mechanistic	To identify changes in immune responses occurring in those responding to ECP therapy compared to non-responders to ECP and untreated controls to identify a beneficial mechanism of action	Immune cell phenotyping transcriptomics analysis of circulating leucocytes, serum cytokine analysis and measures of immune tolerance and apoptosis
	To determine if CLAD phenotype, clinical factors or immune and inflammatory markers in blood alone or in combination can predict likelihood to benefit from ECP	Regression models with responder/non-responder as an outcome and each potential clinical factor or biomarker included as a baseline covariate
Intervention	Nine cycles of ECP therapy administered at 0, +2, +4, +6, +8, +10, +12, +16 and +20 weeks. Each cycle consists of 2 ECP treatments on consecutive days	
Formulation, Dose & Route of Administration	Methoxsalen (UVADEX®) 20 micrograms/ml solution for blood fraction modification used in conjunction with the THERAKOS CELLEX Photopheresis System®	
	Administered via injection into the recirculation bag of the THERAKOS CELLEX Photopheresis System® prior to the photoactivation phase of ECP treatment	
	Dose 0.017mls methoxsalen per ml blood volume treated at ECP	
	Total dose administered is calculated according to buffy coat treatment volume per individual ECP treatment	

Contents

Clinical Trial Protocol	1
RESEARCH REFERENCE NUMBERS	2
PROTOCOL APPROVAL SIGNATURE PAGE.....	3
PROTOCOL ACCEPTANCE SIGNATURE PAGE.....	4
KEY TRIAL CONTACTS.....	5
TRIAL SUMMARY	10
GLOSSARY OF ABBREVIATIONS.....	17
1. BACKGROUND AND RATIONALE	20
1.1 Background.....	20
1.2 Rationale	21
1.3 Risk Assessment	22
2. OBJECTIVES AND OUTCOME MEASURES.....	23
2.1 Primary Objective.....	23
2.2 Secondary Objectives	23
2.3 Sub-Studies.....	23
2.3.1 Mechanistic Sub-study.....	23
2.3.2 Qualitative Sub-study.....	24
2.3.3 Health Economic Evaluation	24
3. TRIAL DESIGN	25
3.1 Summary of Trial Design	25
3.2 Trial Setting	25
3.3 Flow Charts of Study Design and Research Activity	26
3.3.1 Overview of Study Design	26
3.3.2 Flow Chart of Research Activity	27
3.4 Primary and secondary outcome measures/endpoints	28
3.4.1 Primary outcome measure	28
3.4.2 Secondary outcome measures.....	28

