2.3 Sub-Studies

2.3.1 Mechanistic Sub-study

A mechanistic evaluation of participants' immune responses will be undertaken to understand how these change before and after commencing ECP therapy and identify if there are any molecular or cellular markers at baseline which help predict which patients treated with ECP are more likely to respond.

Mechanistic Objectives

- To characterise immune responses occurring in recipients responding to ECP compared to non-responders, and those receiving SOC alone, to identify potential mechanisms of action.
- To determine if CLAD phenotype, clinical factors, or immunological markers in blood can predict who will benefit from ECP.

Further details of outcome measures being collected to answer mechanistic objectives are detailed in 6.1.2.

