6.1.1 Newcastle Mechanistic Cohort

Participants from the Newcastle site only who are enrolled in the ECP+SOC arm will be invited to provide additional blood samples immediately pre and post treatment cycle of ECP on 3 occasions. This will allow for analysis of immune tolerance and apoptotic cells throughout ECP treatment.

During the recruitment process for the main trial, participants from this site will be asked to consent to participate in this additional research blood sampling.

The following research bloods sample, will be taken immediately before ECP on day 1 and immediately after ECP on day 2 of ECP treatment cycles 1, 7 and 9 (week 0, 12 and 20).

- 20ml of whole blood in two EDTA tubes before ECP on day 1
- 20ml of whole blood in two EDTA tubes after ECP on day 2

Processing of blood samples at site:

- Tubes should be mixed immediately after collection by gentle inversion 8-10 times.
- Samples should be stored between 2-5 C in a fridge
- The laboratory staff should be contacted to arrange immediate collection

Note: Where possible please notify the laboratory staff prior to the sample collection to allow for immediate collection and transfer to the processing laboratory at Newcastle University.

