10.1 Sample Size Calculation

Our proposed sample size is 90 patients. We used published evidence to underpin our sample size calculations. Todd et al reported changes in longitudinal lung function in 213 CLAD patients who did not receive ECP; 27% had a <10% loss in FEV1 within 6 months, equating to stabilisation. We assume conservatively that in the SOC arm, 30% patients will be responders. The three largest ECP in CLAD studies show 54-61% patients had <10% decline in FEV1 within 6 months; we therefore assume a 55% stabilisation rate in the ECP arm. With 90 patients randomised 1:1 between SOC and ECP arms, we would have 80% power (5% one-sided type I error rate) to detect a difference when the ECP arm has a 55% response rate and the SOC arm a 30% response rate. This calculation assumes Barnard's exact test is used in the analysis.

As the primary endpoint is a composite responder endpoint, our primary analysis will utilise the augmented binary method to test the difference in response rate as the primary analysis (see Section 10.10.2). Previous work has shown that the augmented binary method increases the power of the analysis equivalent to increasing the sample size by at least 35% without any inflation in the type 1 error-rate. Even allowing for 10% of patients dropping out, we are thus confident power will be above 85% for this analysis, and believe it is likely to be above 90%. Conservatively, for the augmented binary analysis we believe the maximum number of patients required to achieve 80% power is 68.

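### The mechanistic power figures are single-test values printed beside a 5% FDR rule, and the objective on who benefits from ECP is paired with marker models that name no treatment term

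*Protocol*

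**What the plan says.** **Power.** Protocol section 10.3.3 assumes that "50% of patients are responders" and concludes that "we will have 90% power to detect standardised effect sizes of 0.7". A second figure covers the Newcastle cohort alone, where the text reads: "we anticipate a sample size of around 16, which would provide 90% power to detect standardised differences of 1.6". No alpha, sidedness or group sizes are given for either figure. The paragraph then ends: "A multiple testing correction will be applied to ensure that the false discovery rate is controlled at 5" per cent. The number of markers is not stated.

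**Objectives.** The first objective in section 2.3.1 begins "To characterise immune responses occurring in recipients responding to ECP compared to non-responders" and goes on to add the SOC-alone group. The second asks whether phenotype, clinical factors or blood markers predict who benefits from ECP. For that second objective, the mechanistic rows of the Trial Summary name this method: "Regression models with responder/non-responder as an outcome and each potential clinical factor or biomarker included as a baseline covariate". Analysis 1 in section 10.3.3 repeats it for biomarkers, one per model.

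**Related analyses.** Analysis 2 fits longitudinal models in all patients and then within each arm. Analysis 5 looks for a signature of the ECP+SOC v SOC treatment effect. The additional Newcastle samples come from "Participants from the Newcastle site only who are enrolled in the ECP+SOC arm" (section 6.1.1). Section 10.3.3 calls the whole set exploratory and says that it will inform a later effectiveness study.

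**The concern.** There are two separate problems.

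First, a power figure for one uncorrected test stands in the same paragraph as a rule that every marker result must pass a 5% FDR threshold. If the printed 90% already uses the whole 5% level, any correction takes it below 90%. The figure also appears to need both arms pooled, whereas part of the first objective lies within the ECP arm. A reader of the final report could then take a null marker result for a well-powered negative.

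Second, a regression of response on a baseline marker, with no treatment term, finds markers of stability whatever the treatment. A marker that predicts stability equally well on SOC would be reported under an objective about benefit from ECP, and could be carried into the later trial as a selection marker.

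**Working it through.** **Inputs.** "With 90 patients randomised 1:1 between SOC and ECP arms" gives 45 per arm (section 10.1). Design response rates are 55% (ECP) and 30% (SOC), also from section 10.1. The 50% responder share, the effects 0.7 and 1.6, the Newcastle 16 and the 5% FDR are from section 10.3.3.

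**Formula.** For groups n1 and n2 and standardised difference d, the noncentrality is δ = d·√(n1·n2/(n1+n2)). Power is P(T > t[1−α/2]) for a noncentral t with n1+n2−2 degrees of freedom, or Φ(δ − 1.960) by normal approximation at two-sided 5%.

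**Step 1: reproduce the 0.7 figure.** 45 v 45: δ = 0.7 × √22.5 = 3.320. Normal: Φ(1.360) = 91.3%. t-test: 90.7%, with 0.69 detectable at 90%. A one-sided 5% t-test gives 95.1%, which does not match. The pooled design response rate is (55% + 30%)/2 = 42.5% rather than 50%, but 38 v 52 still gives 90.0%, so the 50% assumption does little harm.

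**Step 2: reproduce the 1.6 figure.** 8 v 8: δ = 1.6 × √4 = 3.2. Normal: Φ(1.24) = 89.3%. t-test: 84.5%, with 1.74 detectable at 90%.

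**Step 3: ECP arm only.** 55% of 45 is about 25 responders, leaving 20. δ = 0.7 × √(500/45) = 2.333. Power is 62.6% before correction, and the effect detectable at 90% is 0.99.

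**Step 4: add 5% FDR.** The panel size and the share π of markers truly associated are not in the protocol, so π is an assumed range. For a large panel under the Benjamini-Hochberg procedure, the per-test level a solves a = 0.05·[(1−π)·a + π·power(a)]. Check at π = 50%, pooled: 0.05 × (0.5 × 0.0214 + 0.5 × 0.834) = 0.0214.

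| Assumed share truly associated | Pooled 45 v 45, d = 0.7 | ECP arm 25 v 20, d = 0.7 | Newcastle 8 v 8, d = 1.6 |
|---|---|---|---|
| 50% | 83% | 36% | 69% |
| 20% | 72% | 18% | 48% |
| 10% | 62% | 10% | 31% |
| 5% | 51% | 4% | 16% |

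The effects detectable with 90% average power over the same rows are 0.76, 0.83, 0.89 and 0.94 (pooled), and 1.10, 1.21, 1.29 and 1.37 (ECP arm).

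**Step 5: the marker model.** Take a marker with d = 0.7 between responders and non-responders in both arms alike, so that it carries no information about benefit from ECP on this scale. The pooled model of analysis 1 flags it in about 91% of uncorrected tests (step 1), or 83% to 51% under step 4. Only a comparison of the two arms' marker effects separates this from benefit. As an approximation, the variances of the two within-arm differences are 1/25 + 1/20 = 0.0900 (ECP) and 1/13.5 + 1/31.5 = 0.1058 (SOC, 30% of 45 responding). The standard error of their difference is √0.1958 = 0.4425. The between-arm difference in d detectable at 90% is (1.960 + 1.282) × 0.4425 = 1.43 for one uncorrected test.

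**The case against.** - **The arithmetic is not wrong.** The 0.7 figure reproduces. What is missing is its label: one test, before correction, arms pooled. This stands, and a reader should not infer a calculation error there.
- **The plan does address benefit.** A reader might infer that nothing in the mechanistic plan can show who benefits from ECP. The protocol does not support that. Analysis 5 targets the treatment effect, analysis 2 is repeated by arm, and analysis 1 in section 10.3.3 claims only association with response. The Trial Summary row allows markers in combination, which a signature serves. The criticism is confined to the method named in that row and its counterpart, analysis 1. Naming no arm term is also not the same as excluding one, and model detail may be in the SAP, but the row fixes a method for an objective that this method, as written, cannot answer.
- **The first objective is wider than the ECP arm.** It includes SOC controls. ECP responders against the whole SOC arm (25 v 45) have about 79% uncorrected power at 0.7. So 63% describes one part of the objective.
- **Newcastle.** That cohort is in the ECP arm by design, so the ECP-only comparison is not ignored there. The size is approximate, and 9 v 9 gives 89% by t-test. A one-sided 5% t-test on 8 v 8 gives 91.8%, but one-sided testing is not stated for these figures and would not match the 0.7. A reader might also take 16 as the site total, leaving 4 v 4 in the ECP arm; the protocol does not say so.
- **The FDR sizes are assumptions, and the tests are simple.** No single FDR-adjusted value follows from the protocol. Repeated samples in analyses 2 and 3 could change the detectable effects.
- **Exploratory status.** No primary or secondary efficacy conclusion depends on these analyses. This limits the consequence but does not make the printed 90% compatible with the correction beside it.

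**Conclusion.** The point holds in limited form. Taken together, the two power figures are right only for single uncorrected two-sided 5% tests, and the Newcastle one only by a normal approximation that overstates power by about 5 points at 8 v 8 (89.3% v 84.5%). Under the plan's own 5% FDR control, pooled power at 0.7 is about 83% to 51% if 50% to 5% of markers are truly associated; that range is assumed. The contrast within the ECP arm has about 63% at 0.7 before correction, and needs about 0.99 for 90%, for a two-group test at one time point with 25 v 20.

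Separately, the Trial Summary ties the objective on benefit from ECP to regressions that, as described, measure prognosis. Analysis 5 is the one analysis aimed at the treatment effect, and it carries no power figure. This should be corrected, but it does not threaten the trial's main conclusions.

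**What to change.** In section 10.3.3:

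- State alpha, sidedness and group sizes, and label 0.7 and 1.6 as per-test, pre-FDR figures.
- For Newcastle, give about 84% at 1.6, or 1.74 detectable at 90%, for 8 v 8 two-sided, and say that the 16 are ECP-arm participants if that is meant.
- Add the ECP-arm detectable effect (about 0.99 for a simple two-group, single-time-point test) and an FDR-adjusted figure or range for the planned panel, with the assumed share of true markers stated.

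In analysis 1 and the matching Trial Summary row, fit response on arm + marker + arm × marker. Report the interaction as the exploratory single-marker test of benefit, alongside analysis 5, and the main effect as prognostic.

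The cost is protocol and SAP wording and two model terms, with no new data. The downside is low power for the interaction: by the approximation in step 5 of the working, a between-arm difference of about 1.4 is needed for 90% even before correction. The plan should say so, so that a null interaction is not read as evidence that a marker has no predictive value.

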10.3.4 Subgroup Analyses

We will conduct subgroup analyses (carried out in a similar manner to that of the primary analyses, as described above) to explore the consistency in the efficacy of ECP between the three CLAD phenotypic subgroups. We note that this is exploratory, and the trial sample size has not been chosen to ensure this analysis is well-powered. Subgroup analyses will only take place where it is judged that the available sample size is sufficient for the proposed analysis.

10.3.5 Missing data

We will assess the impact of missing primary outcome data by examining its extent, and whether it is missing at random or is informative. We will consider the use of multiple imputation methods and sensitivity analyses if data is considered missing to a sufficient extent (e.g. approximately >10%). Similar consideration may be made for secondary outcome measures.

10.3.6 Interim Analyses and Criteria for the Premature Termination of the Trial

There is no formal interim analysis. An IDMC of all independent members will be convened to undertake independent review.

11. DATA HANDLING

11.1 Data Collection Tools and Source Document Identification

All data for an individual patient will be collected by each PI or their delegated nominees and recorded in the electronic case report form (eCRF) for the study. The study-specific eCRF will be set up using Redpill, Sealed Envelope's eCRF system. Participant identification on the eCRF will be through a unique trial identifier. Participants cannot be identified from eCRFs or paper data collection tools. The participant's name will be linked to their unique trial identifier via a record filed within each site's ISF, which will be stored in a locked room at site.

A Source Data Agreement will be completed prior to each site opening to screening and recruitment activity; this will document agreed sources of data.

11.2 Data Handling and Record Keeping

The CI has overarching responsibility for collection, quality and retention of data. Data will be collected by an appropriately qualified and delegated member of site personnel. Data will be handled, computerised and stored in accordance with the UK Data Protection Act 2018 and the UK GDPR as amended on 01 January 2021 by regulations under the European Union (Withdrawal) Act 2018, to reflect the UK's status outside the EU, the latest GCP Directive (2005/28/EC) and local site policy. Paper copies of trial-related documentation will be annotated, signed, dated and filed in the Investigator Site

File. Copies of the Summary PIS, PIS, completed written consent form, eligibility forms and letter to GP will be filed in the participant's medical notes.

The CI or designated nominees will continuously monitor completeness and quality of data collected on the trial database. Monitoring will include regular correspondence with site staff to ensure missing data is collected wherever possible and ensuring continuous high quality of data capture. Data completeness and progress reports will be generated for regular review at TMG meetings.

11.3 Access to Data

The site PI and staff formally delegated to do so will have access to source data and the ISF to conduct the trial.

Access to the trial database will be password-limited, with task-specific restrictions (e.g. data entry/randomisation). The site PI will formally delegate database tasks to site staff, by way of dated signatures on the Site Delegation Log.

NCTU trial management staff, representatives of the host institution, Sponsor and the MHRA will be granted access to the source data, ISF and trial database for the purposes of monitoring, audit and inspection respectively. Consent will be sought from the participant for access to their medical records and trial data for the purposes of monitoring, audit and inspection.

Data may be securely downloaded from the trial database and released to the Trial Statistician for analysis, including, as needed, for reports to the IDMEC. Data release will only take place after documented agreement from key members of the TMG.

Site staff, including the PI may not disclose or use for any purpose other than conduct of the trial any data, record or other unpublished confidential information disclosed to those individuals for the purpose of the trial. Prior written agreement from the Sponsor or its designee must be obtained for the disclosure of any said information to other parties.

11.4 Archiving

Trial documents and data will be archived in accordance with UK GCP legislation and as specified in Sponsor and NCTU SOPs. All trial documentation and data will be archived for 5 years.

12. MONITORING, AUDIT & INSPECTION

12.1. Trial Management Group (TMG)

The TMG will be responsible for the day-to-day running of the trial and will consist of the CI, members of NCTU, statistician(s), Sponsor and, as required, other members of the co-applicant team. The TMG will monitor all aspects of the conduct and progress of the trial, ensure that the protocol is adhered to and take appropriate action to safeguard participants and the quality of the trial itself. TMG meetings will occur approximately 4-6 weekly. Progress will be monitored proactively according to agreed trial timelines and any issues addressed. The TMG will liaise with the Trial Steering Committee (TSC), providing updates on trial progress and highlighting any issues arising.

12.2. Trial Steering Committee (TSC)

The TSC will be established to provide overall independent oversight of the trial and will oversee trial conduct and progress. The TSC will consist of an independent chair, together with at least two other independent members, a Patient and Public Involvement (PPI) representative and the Chief Investigator. The TSC will meet approximately 6-monthly throughout the trial and meetings may be attended by non-voting observers including those from the NCTU, co-applicant team, Sponsor and Funder.

12.3. Independent Data Monitoring and Ethics Committee (IDMEC)

The IDMEC (also referred to as DMC and IDMC) will consist of at least three independent members including an Independent Chair, an Independent Statistician and an Independent Clinician. The IDMEC will make recommendations to the TSC as to whether there are any ethical or safety issues that may necessitate changes to the trial. The IDMEC will meet approximately 6-monthly throughout the trial.

